2.4.1 Risks of IVIG

Like the FLU-IVIG Pilot, the IVIG used in this study will be manufactured in the same manner and to the same standards as commercially available (non-influenza antibody enriched) IVIG. This includes screening for blood-borne pathogens and manufacturing steps that include solvents/detergents to inactivate any viruses. There are no anticipated unique risks to an anti-influenza antibody enriched IVIG; therefore the risks are anticipated to be the risks of standard IVIG preparations. Common risks include fever, rash, hives, or headache. Other more serious risks are rare and include serious allergic reactions including anaphylaxis, hemolysis, and aseptic meningitis. As IVIG is made from human plasma, transmittable viral infections such as hepatitis B, hepatitis C, and human immunodeficiency virus (HIV) are a potential risk, although steps are taken to screen for and inactivate such pathogens. In addition, there is a theoretical risk, although low, that IVIG administration may be capable of transmitting other known or unknown infectious agents other than viruses, such as infectious prions (e.g., the agent of Creutzfeldt-Jakob disease).

Immune globulin administration may impair the efficacy of live attenuated virus vaccines such as measles, rubella, mumps and varicella. Renal dysfunction, acute renal failure, and osmotic nephropathy may occur with immune globulin intravenous products in predisposed patients. Renal dysfunction and acute failure occur more

commonly in patients receiving IVIG products containing sucrose. The influenza IVIG preparation used in this study does not contain sucrose.

Although rare, transfusion-related acute lung injury (TRALI) may occur with IVIG therapy and is characterized by severe respiratory distress, pulmonary edema, hypoxemia, normal left ventricular function, and fever.

There are case reports of pulmonary emboli occurring after administration of IVIG and plasma therapy, although definitive studies assessing risk are lacking.³² In one series 5 of 10 patients critically ill with A(H1N1)pdm09 were shown to have pulmonary emboli.³³ This high percentage has not been shown in other H1N1 series, and pulmonary emboli have been shown to develop in approximately 10-15% of critically ill adults.³⁴ However, the potential risk of pulmonary embolism exists. Other thrombotic events, including myocardial infarction, cerebral vascular accident, and deep vein thrombosis may also occur.

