4.2.5 Reporting of Adverse Events

INSIGHT 006: FLU-IVIG

As noted in section 2.4.1 there are potential risks associated with taking IVIG. These risks include fever, rash, hives, headache, allergic reactions, transmitted infections, renal dysfunction/failure, TRALI and pulmonary embolism. The risk of transmitted infections is considered low because of the screening of the plasma used to make the IVIG.

Some of these risks are similar to symptoms associated with influenza. Also, it is expected that many participants will have co-morbid conditions that are associated with signs, symptoms and laboratory abnormalities that are similar to possible risks of IVIG. Thus, AEs will be collected irrespective of perceived relationship to treatment in order to compare differences between the IVIG and placebo groups.

Through 28 days of follow-up, AE data collection will be restricted to any new grade 3 or 4 AE, or previously existing AEs which have increased in severity to grade 3 or 4.

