If a NEW score is not available on Day 3, the last available follow-up NEW score will be used.

For the favorable outcome on Day 7, for the 4 participants who are missing the primary outcome on Day 7, it is presumed that they did not die or were re-hospitalized following discharge, i.e., they will be considered as having a favorable outcome.

H. Supportive Efficacy Endpoints

The following efficacy outcomes are defined as supportive:

- Time to discharge
- Time to death
- Percentage alive and out of the hospital at day 28
- Change in nasopharyngeal viral load from baseline to day 3
- Change in HAI titers from baseline to day 1, 3 and 7
- Percentage dying or requiring re-hospitalization after discharge
- Percentage with a diagnosis on or after the day of randomization and before the day 28 visit developing acute respiratory distress syndrome, acute renal failure, sepsis, pneumonia, enteritis or bronchitis (considered individually and also any of the diagnoses)
- Ordinal outcome on day 14
- Percentage alive and out of the hospital at day 14
- Resumption of normal activities at day 14.
- Ordinal outcome on day 28

Analysis Considerations for Supportive Efficacy Outcomes

Kaplan-Meier curves will be used to summarize the time to discharge and time to death, overall and through 7 days. The median number of days from randomization to discharge will be estimated. Deaths during hospitalization will be censored after day 28 (or day 7) for analyses of time to discharge. A logrank test will be used to compare treatment groups.

For participants who experienced multiple hospitalizations during follow-up, the time to the last discharge before day 28 will be considered. As the visit window for the day 28 visit extends to day 35, events after day 28 but prior to the final visit will be included in these analyses.

The difference between the IVIG and placebo group for change in log-transformed nasopharyngeal viral load from baseline to day 3 will be summarized using stratified analysis of variance with baseline viral load as a covariate. Viral loads vary by subtype. Therefore, strata will be defined by influenza virus subtype (H1N1, H3N2, or B) as well as geographic region. In these analyses, levels below 75 copies, the lower limit of detection, will be imputed as 75 copies. For this analysis, deaths (currently one

participant) on or before day 3 will be excluded, as will participants with undetectable RNA.

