The IVIG and placebo group will also be compared for the percentage with undetectable viral RNA at day 3 using logistic regression with baseline viral load as a covariate and geographic region and influenza subtype as stratifying factors. For this analysis, exclusions will be as per the previous paragraph; however, participants dying on or before day 3 (currently one participant) will be included in these analyses and considered as having detectable RNA.

Ordinal outcomes will be summarized using a proportional odds model as described for the primary ordinal outcome (see E.).

Binary outcomes will be summarized with logistic models that are stratified by geographic region and include indicators for the participant's clinical status at entry (ICU, general ward on supplemental oxygen, general ward not on supplemental oxygen), and an indicator for whether the participant was in the IVIG pilot trial (FLU 005) or the FLU-IVIG trial (FLU 006).

Reference viruses used for HAI titers changed over the course of the study corresponding to the circulating viruses. Longitudinal random effects models stratified by subtype (H1N1, H3N2, B) will be used to estimate differences in log-transformed HAI titers between the IVIG and placebo group at days 1, 3 and 7. Baseline HAI levels will be included in these models as a covariate. Each HAI titer assessed will be used to compare the two treatment groups. In addition, analyses specific to the virus of infection, will be carried out. For participants infected with H1N1, A/California/2009 and A/Michigan/2015 will be used; for those infected with H3N2, A/Hong Kong/2014, A/Switzerland/2013 and A/Texas/50/2012 will be used; and for those infected with influenza B virus, B/Phuket/2013, B/Brisbane/2008 and B/Massachusetts/2012 will be used.

I. Safety Endpoints

Targeted symptoms are collected at baseline day 3 and day 7. Unsolicited grade 3 or 4 adverse events are collected on days 1-3, 7, 14, and 28. SAEs are collected throughout the 28 day follow-up. The following will be summarized:

- Percentage of participants for whom infusion was interrupted.
- Percentage of participants with adverse events of grade 3 or 4 severity.
- Percentage of participants with a serious adverse event (SAE).
- Percentage with a composite outcome of death, SAE, infusion interruption, or any grade 3 or 4 adverse event.
- Percentage of participants with each targeted symptom on day 3 and on day 7

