- Change in serum chemistries and complete blood count (CBC) between baseline and day 7.

Analysis Considerations for Safety Outcomes

Adverse events will be compared for the IVIG and placebo groups and summarized using chi-square statistics stratified by geographic region. Serum chemistry and CBC measurements will be summarized as changes from baseline to Day 7 using analysis of covariance stratified by clinical site (local laboratories were used).

J. Baseline Characteristics

Tabulations will be prepared by treatment group for a number of baseline variables:

- Influenza subtype
- Age
- Gender
- Race/ethnicity
- Enrollment ward/use of O₂
- Geographic region
- Northern/Southern hemisphere/Equatorial
- Duration of symptoms prior to randomization
- New score
- Influenza season
- Co-morbidities
- Complications
- Subtype/viral load as defined for subgroups
- Influenza vaccination
- Smoking status
- Use of antiviral medication at time of randomization and of those given antivirals the percentage given oseltamivir.

Summary statistics will include N, mean, SD, median, 25th, 75th percentiles, and percentages for categorical variables. Categorical variables will be defined as for the subgroup analysis.

K. Infusion Summary

The following statistics will be used to summarize the infusion in each treatment group:

- Number and percentage of participants receiving complete infusion, partial infusion, or not infused.
- Among participants infused, the day of infusion (same day as randomization, next day, > 1 day after randomization).
- Among participants infused, time between randomization and beginning of infusion (median minutes, 25th, 75th percentiles).
- Among participants infused, estimated dosage administered (median mL, 25th, 75th percentile).
- Among participants receiving full infusion, duration of infusion (median minutes, 25th, 75th percentiles).
- Number and percentage of participants with a grade 3/4 AE or SAE during the infusion.

- Listing of problems reported during the infusion.

L. Completeness of Follow-up

According to protocol, participants are to be seen for data collection at day 1, 3 and 7 after randomization. In addition, data collection (by telephone or in person) was required at day 2, day 14, and day 28. The completeness of follow-up will be summarized by treatment group with the following statistics for the participants infused:

- Number and percent of participants attending each required visit.

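### SAP section I compares adverse events only as pooled totals, so no serious IVIG risk named in the protocol has its own event comparison under safety, and acute renal failure is compared as an event only under efficacy

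*SAP*

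**What the plan says.** Protocol 2.4.1 sets out the risks of IVIG. The rarer serious ones include "serious allergic reactions including anaphylaxis, hemolysis, and aseptic meningitis". On the kidney it says: "Renal dysfunction, acute renal failure, and osmotic nephropathy may occur with immune globulin intravenous products in predisposed patients". It describes TRALI and pulmonary embolism, and adds: "Other thrombotic events, including myocardial infarction, cerebral vascular accident, and deep vein thrombosis may also occur". Protocol 4.2.5 gives a shorter list ("fever, rash, hives, headache, allergic reactions, transmitted infections, renal dysfunction/failure, TRALI and pulmonary embolism"), notes that some of these resemble influenza or co-morbid illness, and concludes: "AEs will be collected irrespective of perceived relationship to treatment in order to compare differences between the IVIG and placebo groups". Comparing safety is secondary objective d in protocol 3.3.2.

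SAP section I lists infusion interruption, "Percentage of participants with adverse events of grade 3 or 4 severity", any SAE, a composite of these with death, each targeted symptom on days 3 and 7, and laboratory change. Adverse events are to be compared by region-stratified chi-square, with no categories given. For the laboratory data: "Serum chemistry and CBC measurements will be summarized as changes from baseline to Day 7 using analysis of covariance".

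SAP section H, under supportive efficacy, includes the percentage "developing acute respiratory distress syndrome, acute renal failure, sepsis, pneumonia, enteritis or bronchitis (considered individually and also any of the diagnoses").

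SAP section K adds, by arm, the number with a grade 3/4 event or SAE during the infusion, and a listing of infusion problems.

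**The concern.** The protocol's reason for collecting events regardless of attribution is that an IVIG harm can look like influenza, so only a comparison between arms can reveal it. A total over all grade 3/4 events or all SAEs does this poorly in hospitalized patients, because the disease and its co-morbidities can be expected to supply most of the events. A modest excess of one specific harm then changes the total very little.

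Renal failure raises a second issue. It is a named IVIG risk, yet as an event it appears only among outcomes that IVIG is hoped to reduce. In the any-diagnosis row, extra renal failures on IVIG and fewer pneumonias on IVIG work against each other.

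If no list of named risks is fixed in advance, any grouping of thrombotic, hemolytic or hypersensitivity events would have to be chosen after the arms are known.

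**Working it through.** **1. Each named risk against the SAP**

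| Risk (protocol 2.4.1) | Own event comparison in SAP I | Elsewhere in the SAP |
|---|---|---|
| Pulmonary embolism, MI, stroke, DVT | None | None by type |
| Hemolysis | None | Only indirectly, as mean change in hemoglobin and bilirubin (section I; panel in protocol Appendix B) |
| Anaphylaxis, serious allergy | None | Infusion-period totals and problem listing (section K) |
| Aseptic meningitis | None | None by type |
| TRALI | None; an SAE at any grade (protocol 4.2.2), so it enters the SAE total | None by type |
| Acute renal failure | None as an event; mean change in creatinine and BUN | Section H, individually and in the any-diagnosis row |

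ARDS is also in section H, individually and in the any-diagnosis row. Any renal failure or ARDS that is grade 3/4 or serious also counts in the section I totals, but cannot be told apart there.

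**2. Is there a planned figure to reproduce?** The documents give no event rate, detectable difference or power for any safety comparison. As a check on the two-proportion formula used below, the SAP's favorable-outcome figure (73.5% v 86%, stated power 0.80) gives 0.802 with 162 per arm (324/2).

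**3. Dilution in a pooled endpoint.** Inputs: 308 participants (SAP section D), taken as 154 per arm (assumed from 1:1 allocation); two-sided 0.05. All event rates are assumptions.

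A named risk, or the named risks as a group, compared alone (exact Fisher power against 1% on placebo):

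| IVIG rate | 2% | 3% | 4% | 5% | 6% | 7% |
|---|---|---|---|---|---|---|
| Power | 2% | 10% | 24% | 41% | 58% | 72% |

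For the same excess inside an any-event endpoint with background b in both arms, the rates are b and b + 0.05(1 − b). Power = Φ[(d − 1.96·SE0)/SE1], where d is the difference, SE0 the pooled standard error and SE1 the unpooled one. Worked for b = 25%:
- Rates 0.25 and 0.25 + 0.05 × 0.75 = 0.2875, so d = 0.0375.
- SE0 = √(2 × 0.26875 × 0.73125/154) = 0.0505.
- SE1 = √[(0.25 × 0.75 + 0.2875 × 0.7125)/154] = 0.0505.
- Power = Φ[(0.0375 − 0.0990)/0.0505] = Φ(−1.22) = 11%.

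| Background | 15% | 25% | 35% |
|---|---|---|---|
| Power, 5-point excess (1% v 6%) | 17% | 11% | 9% |
| Power, 6-point excess (1% v 7%) | 22% | 14% | 11% |

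Placing 1% and 6% on top of the background in both arms gives 16%, 11% and 9%.

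**4. Offset in a pooled endpoint.** Assume a harm at 1% placebo v 5% IVIG, and other events at 20% placebo v 15% IVIG, independent of the harm:
- Placebo: 1 − 0.80 × 0.99 = 20.8%.
- IVIG: 1 − 0.85 × 0.95 = 19.25%.

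The pooled result leans towards IVIG although the specific harm is five times as frequent. This applies to the any-diagnosis row and the section I composites. It does not apply to renal failure or ARDS taken individually.

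**5. What a direct comparison can show.** Against zero events on placebo, Fisher p is 0.060 for 5 on IVIG and 0.030 for 6. Zero events in 154 has an exact upper 95% limit of 1 − 0.025^(1/154) = 2.4%. The interval is therefore informative even where the test is not.

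**The case against.** The strongest reply is that the SAP covers more than totals. Targeted symptoms are compared one by one, although the symptom list is not in the documents and its overlap with fever, rash or headache cannot be checked. Creatinine, BUN, bilirubin and hemoglobin are compared in section I. Section K looks at the infusion period, when acute hypersensitivity would be expected. A reader might infer that the SAP compares none of the named risks; these items show that this goes too far.

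A reader might also infer that filing renal failure and ARDS under efficacy dilutes or cancels a harm. For those two diagnoses it does not. Each has its own between-arm comparison, by a logistic model adjusted for entry status and stratified by region, and the label does not alter the estimate. Nor does the SAP score TRALI or acute lung injury as efficacy: the listed diagnosis is ARDS, and whether a TRALI case would be recorded there is not stated.

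The assumed excess is also open to challenge. Protocol 2.4.1 calls the serious risks and TRALI rare and the product sucrose-free, and protocol 3.8.2 excludes patients judged at substantially increased thrombotic risk. With a smaller excess, the direct comparison is weak too. That stands, and it is why the power contrast is only an illustration.

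Finally, the SAP calls itself a general strategy and does not forbid tables by type, and the DSMB may judge event frequencies in aggregate (protocol 4.2.3). So the documents do not support a prediction that a harm would be misreported. But a table that is merely not forbidden is not prespecified, and mean change at Day 7 is a poor detector of a few large or transient abnormalities.

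**Conclusion.** The point holds as a gap in the safety analysis. Followed as written, SAP section I gives no event comparison for any serious IVIG risk named in protocol 2.4.1. Thromboembolism, hemolysis, anaphylaxis, aseptic meningitis and TRALI have none anywhere in the SAP beyond general infusion-period summaries. Acute renal failure has one, but only under efficacy, where its any-diagnosis row can mix harm with benefit.

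The size depends on assumed rates: 58% power alone against about 9-17% pooled for 1% v 6%, and only 2-24% alone for 1% v 2-4%. The case for change therefore rests on having prespecified estimates with intervals, not on gaining a powerful test. Nothing here shows that a harm exists, or that the efficacy conclusions would change.

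**What to change.** In SAP section I, before unblinding:

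- Prespecify a list of the protocol's named IVIG risks: thromboembolic events, acute renal failure, hemolysis, TRALI, anaphylaxis/hypersensitivity and aseptic meningitis. Code it blind to arm from the AE, SAE and diagnosis data already collected. Report counts by arm with exact 95% confidence intervals, by type and as a group.
- Repeat acute renal failure and ARDS under safety, and show the any-diagnosis row of section H with and without them.
- Beside mean laboratory change, tabulate by arm the number with a prespecified worsening in creatinine, hemoglobin and bilirubin at Day 7. Use DAIDS grades where local reference ranges are available, and fold or absolute change otherwise.

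The cost is SAP wording, a term list, blinded coding and a few tables, with a few more descriptive comparisons to interpret. Some things cannot be recovered. Protocol 4.2.5 restricts AE collection to grade 3 or 4, so non-serious events below that grade will still be missed. So will transient laboratory changes before Day 7, the only scheduled follow-up laboratory visit in protocol Appendix B.

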3.9.3 Storage and Administration of Study Treatment

After a site is opened for enrollment, a supply of IVIG will be provided to the clinical site pharmacy. Details for storing, labeling, and dispensing study treatment are detailed in the *INSIGHT FLU-IVIG Pharmacy Manual*.

Administration of blinded study treatment will commence as soon as possible after randomization on the day of randomization (Day 0). The study treatment will be administered in a single infusion with a total volume of 500 mL over approximately 2 hours.

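### SAP section I plans no by-arm comparison of grade 3/4 adverse events, SAEs or the safety composite in an early window after the single infusion

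*SAP*

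**What the plan says.** The protocol gives treatment once: "The study treatment will be administered in a single infusion with a total volume of 500 mL over approximately 2 hours" (section 3.9.3). On adverse events, protocol section 4.2.5 says "Through 28 days of follow-up, AE data collection will be restricted to any new grade 3 or 4 AE", or an existing event that worsens to those grades. Events are recorded whatever their perceived cause, so that the arms can be compared. The same section concedes that "Some of these risks are similar to symptoms associated with influenza".

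SAP section I describes collection in two sentences: "Unsolicited grade 3 or 4 adverse events are collected on days 1-3, 7, 14, and 28" and "SAEs are collected throughout the 28 day follow-up". Its endpoints include "Percentage of participants with adverse events of grade 3 or 4 severity", the percentage with an SAE, and "Percentage with a composite outcome of death, SAE, infusion interruption, or any grade 3 or 4 adverse event". No time window is attached to any of them. The test is a chi-square stratified by geographic region.

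The one narrower window for graded events or SAEs is in SAP section K: "Number and percentage of participants with a grade 3/4 AE or SAE during the infusion", tabulated by treatment group.

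Other parts of the plan also look early:
- infusion interruption, each targeted symptom on Days 3 and 7, and chemistry and blood-count change to Day 7 (section I);
- two Day 3 ordinal outcomes that use death, ICU stay, and NEW score or oxygen (section G);
- time to death through 7 days (section H).

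**The concern.** Exposure happens once, on or near Day 0. Protocol section 2.4.1 names allergic reaction, hemolysis and TRALI among the risks of IVIG, and section 4.2.2 makes every TRALI an SAE. Such events could plausibly appear after the infusion has ended but within a few days. The patients are acutely ill and may have graded events from influenza or co-morbidity throughout follow-up.

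Cause is deliberately set aside when events are collected, so timing is one of the few remaining ways to separate a product effect from the disease. A per-participant proportion over the whole collection period discards it. A reaction on Day 1 and a complication on Day 15 count alike, and a participant who has both counts once.

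At stake is what a null safety result would mean. If the 28-day comparison has little power for an acute excess, no difference between arms is weak reassurance. If IVIG also prevents later influenza complications, as the trial hopes, the benefit could cancel an early excess in the same table.

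**Working it through.** The plan states no rate, power or expected count for any adverse-event comparison, so there is no figure of its own to reproduce. The sample size of 320 was set for the Day 7 ordinal outcome and does not enter here. What follows illustrates the size of the effect under stated assumptions.

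**Inputs**
- n = 154 per arm: the 308 in SAP section D, assumed to split equally.
- Two-sided alpha of 0.05.
- Assumed background risk p0: 5% by Day 3 and 25% by Day 28.
- Assumed excess e: the fraction of IVIG recipients with an early event caused by the product, independent of background events.

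**Formulas**
- IVIG risk: p1 = 1 − (1 − p0)(1 − e).
- Power = Φ[(p1 − p0 − 1.96·se0)/se1], with p̄ = (p0 + p1)/2, se0 = √(2p̄(1 − p̄)/n) and se1 = √((p0(1 − p0) + p1(1 − p1))/n).

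**Worked case, e = 7%**
- Through Day 3: p1 = 1 − 0.95 × 0.93 = 0.1165, a difference of 6.65 points. se0 = 0.03148, se1 = 0.03125. Power = Φ[(0.0665 − 0.0617)/0.03125] = Φ(0.15) = 0.56.
- Through Day 28: p1 = 1 − 0.75 × 0.93 = 0.3025, a difference of 5.25 points. se0 = 0.05096, se1 = 0.05087. Power = Φ[(0.0525 − 0.0999)/0.05087] = Φ(−0.93) = 0.18.

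The longer window loses twice. Some participants with a reaction would have had another event anyway, so the difference shrinks, and the higher event proportion raises the variance.

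**Other sizes of excess, same backgrounds**

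| Excess e | IVIG risk, Day 3 | IVIG risk, Day 28 | Power, Day 3 | Power, Day 28 |
|---|---|---|---|---|
| 3% | 0.0785 | 0.2725 | 0.17 | 0.07 |
| 5% | 0.0975 | 0.2875 | 0.36 | 0.11 |
| 7% | 0.1165 | 0.3025 | 0.56 | 0.18 |

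**Other backgrounds, e = 7%.** With 3–10% by Day 3, early power is 0.68 down to 0.37. With 15–35% by Day 28, 28-day power is 0.27 down to 0.13. If background events come early (8% by Day 3, 10% by Day 28), the two powers are 0.43 and 0.37.

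**Offset by benefit, e = 7%.** The later background risk among those without an early event is (0.25 − 0.05)/0.95 = 0.2105. Suppose IVIG cuts this by 20%. The 28-day IVIG risk is then 0.1165 + 0.8835 × 0.2105 × 0.8 = 0.2653, a difference of +1.5 points. With a 30% cut it is 0.1165 + 0.8835 × 0.2105 × 0.7 = 0.2467, a difference of −0.3 points. The early difference stays at 6.65 points in both cases.

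**The case against.** The strongest reply has five parts.

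**The plan already looks early in other ways.** It compares symptoms on Day 3, infusion interruption, laboratory changes to Day 7 and Day 3 clinical status. This stands as a limit on the gap. It does not close it: symptoms are tabulated at fixed days and not as new graded events, and the Day 3 ordinal outcomes measure net status, in which benefit and harm mix.

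**The numbers rest on assumptions.** The documents give no event rates and no onset times. Protocol section 2.4.1 calls the more serious risks rare, and section 2.3 reports no safety concern among 31 pilot patients. It also names renal failure and thrombotic events, which nothing in the documents places within three days. At an excess of 3% both windows have little power, so an early null would also be weak reassurance. All of this stands.

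**The 28-day window is inferred.** The endpoint bullets state no window; it is read from the collection period. This is correct, though neither document offers another reading.

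**Serious reactions have other routes.** SAEs are reported within 24 hours and the DSMB meets every six months. That is monitoring during the trial and does not replace a by-arm comparison in the final analysis.

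**Days 0–3 is not a clean window.** Follow-up days count from randomization (protocol section 3.9.4), while SAP section K allows for infusion the next day or later. This stands and shapes the fix.

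A reader might go further and infer that acute harm would be buried under a month of influenza events, or that the plan has no early safety view at all. The documents do not support the first, because it depends on rates and timing they do not give and the loss is modest when background events cluster early. The comparisons listed above contradict the second.

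**Conclusion.** The omission is real and limited. Neither document specifies a by-arm comparison of incident grade 3/4 events, SAEs or the composite in any window between the infusion itself and the full collection period, although visits on Days 1–3 would supply most of the data for one. For an acute excess, early-window power exceeded 28-day power in every case above. The margin ranges from large (0.56 against 0.18) to small (0.43 against 0.37), depending on assumed background rates, the timing of background events and the size of the excess. Whether a benefit would mask early harm is likewise conditional on IVIG reducing later events. This is a cheap improvement to the safety tables. It is not an error or a contradiction in the plan, and it does not show that the planned comparison would miss harm.

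**What to change.** In SAP section I, keep the 28-day comparisons and add the same three (grade 3/4 events, SAEs, composite) for events with onset from the start of infusion through a fixed interval, equal in length for every participant; three days after the start of infusion is one example. Counting from the infusion and not from randomization removes the unequal exposure that delayed infusions would create. Use the same region-stratified chi-square, with an exact version where counts are sparse. State the interval before treatment codes are opened, so that the choice cannot follow the data.

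The cost is one extra column in planned tables and a few more safety comparisons, to be read descriptively. Onset dates must be available. The documents do not show the case report form, but the infusion summary in section K already needs event timing. SAP section D excludes those who declined infusion, and both arms receive one, so both share the same time zero.
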